For the subset of the research questions that focus on identifying the causal relationships that drive the outcomes and decisions observed, we will use multivariate analyses such as regression analysis to explore how choices and characteristics impact feeding practice decisions and nutrition outcomes while holding other contributing factors constant. We will use Ordinary Least Squares (OLS) regression, logistic and multinomial logistic regression, survival analysis, quantile regression, and growth models to answer these questions. We will apply OLS regression models to explore how continuous dependent variables are, on average, impacted by background characteristics, experiences, and decisions. We will use Logistic (and multinomial) regression to model how dichotomous (and categorical) decisions and outcomes (e.g., the decision to breastfeed) are impacted by background characteristics, experiences, and past decisions. Similarly, we will use survival analyses to model how background characteristics, experiences, and past decisions affect time duration until an event (e.g., number of day until breastfeeding cessation). Finally, for investigating weight outcomes, we will initially explore the relationships between predictors and outcome using OLS regression but then will use quantile regression to estimate impact that the explanatory variables have on the dependent variable quantiles (we propose using quintiles but will also explore other slices of the distribution). This will provide insight into how the explanatory variables affect each weight/length quintile (top 20 percent of the distribution, etc.) rather than the mean level as OLS regression does. Additionally, we will use growth models to estimate the impact that covariates have on the weigh/length growth trajectory.

---

We will continue to interview women who leave the WIC program with the understanding that there may be a drop off in their interview cooperation rate.

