Table: Percentage of infants and toddlers consuming different types of grain products by age (Months 3-24)	FITSa S42	Both
Table: Percentage of infants and toddlers consuming different types of fruits products by age (Months 3-24)	FITSa S43	Both
Table: Top five fruits consumed by infants and toddlers by age (Months 3-24)	FITSa S44	Both
Table: Percentage of infants and toddlers consuming different types of vegetables by age (Months 3-24)	FITSa S45	Both
Table: Top five fruits vegetables consumed by infants and toddlers by age (Months 3-24)	FITSa S46	Both
Table: Percentage of infants and toddlers consuming meats or other protein sources by age (Months 3-24)	FITSa S47	Both
Table: Percentage of infants and toddlers consuming desserts, sweets, sweetened beverages, and salty snacks, by age (Months 3-24)	FITSa S48	Both
Table: Usual nutrient intake distributions of infants: Micronutrients (Months 3,5 & 7,11)	FITSb S16	Both
Table: Usual nutrient intake distributions of toddlers 12 to 24 months (Months 13-24)	FITSb S17	Both
Table: Estimated energy requirements and usual intake of food energy, infant and toddlers (Months 5-24)	FITSb S17	Both
Table: Usual nutrient intake distributions: Macronutrients (Months 5-24)	FITSb S18	Both
Table: Usual intake of dietary fiber (Months 5-24)	FITSb S19	Both
Table: Mean intakes of selected nutrients by source of milk (Month 5)	FITSb S20	Core
Table: Mean intakes of selected nutrients by source of milk (Month 5)	FITSb S20	Core
Figure: Percentage of infants and toddlers participating in nonmeal eating occasions (Months 7-24)	FITSc S66	Both

Table 7-2. Summary of analyses to be conducted (continued)

Table/Figure (Interview months)	Source	Sample
Nutritional Intake (continued)		
Table: Percentage of total energy from each eating occasion by age category for infant and toddlers (Months 3-24)	FITSc S66	Both
Table: Macronutrient distributions at meals and snacks by age category (Months 7-24)	FITSc S67	Both
Table: Nutrient density: vitamin A, C, D, foliate, Ca, Fe per 1000 Kcals and fiber (Months 7-24)	FITSc S67 and new	Both
Table: Most frequently eaten foods at each eating occasion by age category (Months 3-24)	FITSc S68	Both
Child's Weight and Feeding Practices		
Table: Percentage of children in each weight/length quintile by breastfeeding experience for months 6, 12, and 24 (Months 1, 3 and clinical records 6, 12, 24)	New	Both

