Table: Percentage of children (at 24 months) in each weight/length quintile by timing of the introduction of different types of solid foods (Cumulative; Months 1-13 & clinical records 24)	New	Both
Table: Child's weight/length quintile at 24 months by mothers average sweetened beverage and fruit and vegetable intake score (Month 24)	New	Both
Table: Percentage of children in top 20% and bottom 20% of the weight/length distribution at 12 and 24 months by breastfeeding experience and socio-demographics (Months 1, 3 and clinical records 12, 24)	New	Both
Table: Percentage of children in top 20% and bottom 20% of the weight/length distribution at 12 and 24 months by child's health, physical activity behavior, and rearing/feeding practices (Cumulative, Months 1-24 and clinical records 12, 24)	New	Both
Table: Average child weight/length gain in first 6 months by breastfeeding experience and gender (Months 1, 3 and clinical records 1, 6)	New	Both
Table: Average child weight/length gain in first 6-12 months by breastfeeding experience and gender (Months 1, 3 and clinical records 6, 12)	New	Both
Table: (Model) OLS regression estimates of the impact of the impact of socio-demographics and feeding practices on weight/length at 24 month (Cumulative; Months 1-24 and clinical records for 6, 12 24)	New	Both
Table: (Model) Quantile regression estimates of the impact of socio-demographics and feeding practices on weight/length at 6 month (Cumulative; Months 1-6 and clinical records for 6)	New	Both
Table: (Model) Quantile regression estimates of the impact of socio-demographics and feeding practices on weight/length at 12 month (Cumulative; Months 1-13 and clinical records for 6, 12)	New	Both
Table: (Model) Quantile regression estimates of the impact of socio-demographics and feeding practices on weight/length at 24 month (Cumulative; Months 1-24 and clinical records for 6, 12 24)	New	Both

Table 7-2. Summary of analyses to be conducted (continued)

Table/Figure (Interview months)	Source	Sample
Child’s Weight and Feeding Practices (continued)		
Table: (Model) Growth model estimates of the impact of socio- demographics and maternal health on weight gain trajectory of the child from birth to 2 years (Cumulative; Months 1-24 and clinical records for 0, 6, 12 24)	New	Both

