Introduction of other foods	
 
■ Time until cereal
 
■ Time until fruits
 
■ Time until vegetables
 
■ Time until meats
 
	
 
■ Survival analysis
 
	
 
■ Socio-demographics: Age, race/ethnicity, born in US, household size, income, poverty level, use of child care, returned to work or school, education
 
■ Feeding practices: current use of formula
 
■ Attitudes, beliefs and knowledge: Belief formula provided from WIC is insufficient, parental assessment of baby's weight
 
■ Prenatal experience and advice: Receipt of breastfeeding information from non-WIC sources
 

Table 7-3. Proposed model specifications (continued)

Model	Dependent variable	Estimation methods	Minimum covariates to explore
			
 
■ WIC program experience: Education, time in WIC
 
■ Return to work/school: Returned to work/school within 2 months
 

Weight	
 
■ Child's weight/length (6, 12, and 24 months)
 
	
 
■ OLS
 
■ Quantile regression
 
	
 
■ Socio-demographics: Gender, race/ethnicity, income, born in US
 
■ Maternal/family health: Maternal BMI, paternal obesity, maternal diabetes, smoking during pregnancy, household food security (24 months only), maternal fruit and vegetable dietary intake (24 months only)
 
■ WIC program experience: Education, food package, time in WIC (and peer counseling for 6 month weight/length)
 
■ Child's health and physical activity: birth weight, premature, rapid early weight gain, physical activity indoors, physical outdoors (for 24 month measure) current sleep duration
 
■ Basic dietary intake: Breastfeeding duration, current intake of sweetened beverages
 
■ Feeding practices: Clean plate policy, track eating, careful not to feed too much
 

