59: What is the relationship of infant and child feeding practices to infant and child growth and weight status (e.g., overweight/underweight)?	
Table: Percentage of children in each weight/length quintile at 6, 12 and 24 months by breastfeeding experience (Months 1, 3 and clinical records for 6, 12, 24)
 
Table: Percentage of children in each weight/length quintile at 6, 12 and 24 months by timing of the introduction of different types of solid foods (Months 1-13 and clinical records for 24)
 
Table: Percentage of children in top 20% and bottom 20% of the weight/length distribution at 12 and 24 months by breastfeeding experience and socio-demographics (Months 1, 3 and clinical records 12, 24)
 
Table: Average child weight/length gain in first 6 months by breastfeeding experience (Months 1, 3 and clinical records for 1, 5)
 
Table: Average child weight/length gain between 6-12 months by breastfeeding experience (Months 1, 3 and clinical records for 6, 12)
 
Table: (Model) OLS regression estimates of the impact of the impact of socio- demographics and feeding practices on weight/length at 24 month (Cumulative; Months 1-24 and clinical records for 6, 12 24)
 
Table: (Model) Quantile regression estimates of the impact of socio- demographics and feeding practices on weight/length at 6 month (Cumulative; Months 1-6 and clinical records for 6)
 
Table: (Model) Quantile regression estimates of the impact of socio- demographics and feeding practices on weight/length at 12 month (Cumulative; Months 1-13 and clinical records for 6, 12)
 
Table: (Model) Quantile regression estimates of the impact of socio- demographics and feeding practices on weight/length at 24 month (Cumulative; Months 1-24 and clinical records for 6, 12 24)
 
Table: (Model) Growth model estimates of the impact of socio- demographics and maternal health on weight gain trajectory of the child from birth to 2years (Cumulative; Months 1-24 and clinical records for 0, 6, 12 24)
	New

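### Child weight is categorised only by quintiles of an undefined distribution, so the overweight/underweight part of question 59 has no analysis

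*Combined protocol and SAP*

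**What the plan says.** Appendix B (Table B-1), question 59, asks: "What is the relationship of infant and child feeding practices to infant and child growth and weight status (e.g., overweight/underweight". Ten analyses are mapped to it. The matching block of Table 7-2, on the child's weight and feeding practices, lists twelve: the same ten and two more categorical tables.

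The categorical tables include "Percentage of children in each weight/length quintile by breastfeeding experience for months 6, 12, and 24" and "Percentage of children in top 20% and bottom 20% of the weight/length distribution at 12 and 24 months". Others cross the quintile with the timing of solid foods, with the mother's own intake score, and with child health, activity and rearing practices.

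The only explanation of a quintile is in Section 7.3, on quantile regression. That method is meant to show how explanatory variables "affect each weight/length quintile (top 20 percent of the distribution, etc.) rather than the mean level as OLS regression does". The same paragraph adds: "we propose using quintiles but will also explore other slices of the distribution".

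The remaining analyses are not categorical. Table 7-2 has "Average child weight/length gain in first 6 months by breastfeeding experience and gender" and a companion table for 6 to 12 months. Table 7-3 gives the outcome of the weight model as "Child's weight/length (6, 12, and 24 months", fitted by OLS and quantile regression, and adds a growth model on the repeated measures.

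No growth chart, reference population, z-score or child overweight/underweight cut-off appears. The opening of Chapter 7 promises a comparison with current standards but names none for child weight.

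**The concern.** A quintile is a rank. It says that a child is heavier for length than most children in some distribution, not that the child is overweight. Question 59 asks about weight status and gives overweight and underweight as its example. The plan undertakes to answer all 60 questions, so this part needs at least one analysis that can classify a child.

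The gap matters because early determinants of obesity are a stated reason for the study (Chapter 1), and one of the two conceptual models concerns high early weight (Section 2.3). The plan uses fixed references elsewhere: nutrient intakes are compared with published requirements and upper limits (Section 7.2), and mothers are grouped as overweight, obese or neither (Table C-1). The child's weight has no equivalent.

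A reader of the finished report could take the top 20% to mean overweight, which nothing in the plan supports.

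**Working it through.** The plan gives no sample size, power or prevalence for the weight outcomes, so there is no figure of its own to reproduce. The check is an inventory followed by what the quintile definition implies.

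**Step 1: inventory of the weight block in Table 7-2.**

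| Analysis | Number | What it measures | External reference or threshold |
|---|---|---|---|
| Quintiles, or top/bottom 20% | 5 | Rank in an undefined distribution | None |
| Average gain (0–6 and 6–12 months) | 2 | Mean change | None |
| OLS at 24 months | 1 | Mean weight/length | None |
| Quantile regression at 6, 12 and 24 months | 3 | Quantiles of weight/length | None |
| Growth model, birth to 2 years | 1 | Trajectory | None |

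The total is 5 + 2 + 1 + 3 + 1 = 12. For question 59 in Appendix B it is 3 + 2 + 1 + 3 + 1 = 10. In neither list does any analysis have a reference or cut-off.

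**Step 2: what the overall share can show.** Suppose the cuts are made in the study's own data, separately at each age *a*. Let q₈₀(a) be the 80th percentile of weight/length X at that age. Then

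- P(X > q₈₀(a)) = 0.20 at 6, 12 and 24 months, by definition;
- the share above a fixed reference cut c is 1 − Fₐ(c), which depends on the actual distribution Fₐ.

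The first quantity carries no information about the second. The same holds for the bottom 20% and a low cut.

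**Step 3: what the rows by feeding group can show.** For feeding groups g with population shares w_g and top-quintile percentages p_g, the only constraint is Σ w_g p_g = 20%. The rows may differ. As an illustration, assume two equal groups, normal distributions with a common SD, and means d SD apart. Let c be the pooled 80th percentile, measured in SDs from the lower group's mean. It solves

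0.5[1 − Φ(c)] + 0.5[1 − Φ(c − d)] = 0.20.

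| Assumed d (SD) | Lower group in top 20% | Higher group in top 20% |
|---|---|---|
| 0 | 20.0% | 20.0% |
| 0.1 | 18.6% | 21.4% |
| 0.2 | 17.2% | 22.8% |
| 0.3 | 15.8% | 24.2% |

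Each pair averages 20%; for example (15.8 + 24.2)/2 = 20.0. An association with relative weight is therefore visible in these tables. Whether either group contains more overweight children by an external standard is not.

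**Step 4: are the data there?** Weight and length with dates come from WIC records (Table 3-3), for measurements at 6, 12 and 24 months (Section 4.10). Child sex and date of birth are collected (Table 3-2). These are the inputs needed for an age- and sex-specific weight-for-length z-score.

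**The case against.** The best case for the plan has four parts.

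- **The distribution is not stated to be the study's own.** Table 7-2 lists titles, and the full variable list is in the Database Plan, a separate deliverable. This stands. That the cuts are in-sample and redrawn at each age is a strong inference from Section 7.3 and the table titles, not a stated fact. If a reference distribution is intended, the overall shares could move away from 20%. The plan would still have to name it, and would still have no overweight or underweight cut-off.
- **Quintiles are not the whole weight section.** This also stands. Two descriptive tables report mean gain, and five models use weight/length or its trajectory. They address the growth part of question 59, but none supplies a threshold.
- **The question asks for a relationship, and the tables are split by feeding group.** A reader might infer that a fixed 20% leaves nothing to compare. The documents do not support that: only the overall margin would be fixed, and Step 3 shows that the rows can differ.
- **Overweight/underweight is only an example in the question, and child weight status is not named in the objectives in Section 1.1.** Section 2.4 also presents the antecedents of obesity as a possible extension. This limits the weight of the point. Even so, the example is the question's own account of weight status, and nothing listed addresses it.

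The openness to other slices of the distribution, and the general promise about standards, soften the gap without closing it: neither names a growth reference.

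**Conclusion.** The point holds in limited form. As listed, the analyses can relate feeding practices to relative weight and to growth. They cannot relate them to overweight or underweight, because none of the 12 analyses in Table 7-2, and none of the 10 mapped to question 59, has an external reference or threshold.

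The further statement, that each quintile holds 20% of children overall at every age, rests on two assumptions the plan does not confirm: that the cuts come from the study sample, and that they are made separately at each age.

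A reader might go further and conclude that question 59 cannot be answered at all. That does not follow. The growth part has analyses, and the data for the missing part are already being collected. Nor can one say how many children in the top 20% would fall below an overweight cut-off, because the documents give no prevalence and no cut-off. The group differences in Step 3 rest on assumed mean differences and show only that an association with relative weight remains estimable.

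This should be settled before the weight data are analysed, so that the reference and cut-offs are not chosen with results in view. It does not undermine the rest of the plan.

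**What to change.** Keep the quintile tables, and state which distribution defines the quintiles and whether it is cut separately at each age. Then:

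1. Name a published growth reference and derive each child's age- and sex-specific weight-for-length z-score from it.
2. State the cut-offs for the high and low categories in advance.
3. Add those categories, by feeding practice, to the planned tables at 6, 12 and 24 months.
4. Add the z-score as an outcome in the weight models of Table 7-3.

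The cost is one derived variable, extra rows in tables already planned and an added outcome in models already planned. No new data collection is needed.

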### 2.3 Conceptual Model of Early Childhood Weight Gain

Figure 2-2 depicts a conceptual model of the factors that lead to high weight and potentially early childhood obesity. The childhood weight model was developed based on the literature on early predictors of childhood obesity, showing the factors that affect a child’s risk of obesity.

Figure 2-2. Early childhood weight model

As depicted, maternal and family health characteristics along with socio-demographics affect one’s predisposition to obesity. Similarly, it is believed that early life experiences can affect the “wiring” of the brain, creating a predisposition for obesity. According to this theory, prenatal experiences and feeding practices during infancy can affect the child’s propensity for obesity. Although the factors affecting one’s predisposition to obesity (family characteristics) are largely exogenous, other factors such as infant feeding practices are choices and can be influenced by the WIC program. In addition to the factors that affect a child’s propensity for obesity, there are behavioral factors that directly affect the child’s weight (1) the child’s health and physical activity, (2) the child’s dietary intake, and (3) the feeding practices employed.

The model shows how indicators of obesity can begin with prenatal and family background characteristics, and decisions made about first-year infant feeding. These contribute to both a lifetime propensity for obesity and childhood practices that promote or deter obesity. WIC has the

opportunity to influence this process both during the infant and toddler periods, and through promoting healthy nutrition and behavior during childhood.

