**Table 7-1. Summary of analyses to be repeated from previous studies**

Primary topics	Summary analyses repeated	Analyses not repeated
WIC-IFPS-1		

 
■ Breastfeeding patterns, intensity, and duration
 
■ Reasons for stopping breastfeeding
 
■ Transitional and complementary feeding
 
■ Timing of these decisions
 
■ Supplemental foods
 
	
 
■ Tabulations and comparisons (Chi2 tests) by subgroups (e.g., percentage initiating breastfeeding by socio-demographics)
 
■ Frequencies over time (e.g., percentage still breastfeeding by age of infant)
 
■ Factor analysis (e.g., dimensions for breastfeeding attitudes and knowledge)but items will be updated
 
■ Logistic regressions for probability of an event (e.g., initiating breastfeeding)
 
■ Survival analyses for time until an event (e.g., time until cereals are introduced)
 
	
 
■ Interim models that only use a subset of the covariates
 
■ OLS regressions of breastfeeding frequency (e.g., counts of number of breastfeed at month1)
 

FITS I and II		
Nutrient intake	
 
■ Food and nutrient intake estimates
 
■ Frequencies over time(e.g., percentage consuming vegetables by age of infant)
 
■ One-day nutrient intake distributions (e.g., overall intake and prevalence of inadequate and excess)
 
	
 
■ Tabulations of developmental milestones
 

FDA		
As the FDA study significantly overlaps with the WIC-IFPS-1 and FITS, no additional analyses will be repeated from the FDA study		

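### The 12- and 24-month weight/length models call coefficients impact although WIC terms are adjusted for feeding, diet and early gain, and breastfeeding for early gain and later feeding

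*Combined protocol and SAP*

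**What the plan says.** Section 7.3 lists model estimation under causal analyses and describes regression effects as estimated "while holding other contributing factors constant". In Table 7-2, the OLS row for child weight and the matching quantile row are titled the "impact of socio-demographics and feeding practices on weight/length at 24 month". Quantile rows for 6 and 12 months carry the same wording.

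Table 7-3 (Weight) specifies one model for the child's "weight/length (6, 12, and 24 months"), by OLS and quantile regression. Its single covariate list includes:

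- "WIC program experience: Education, food package, time in WIC (and peer counseling for 6 month weight/length");
- among the child-health items, "birth weight, premature, rapid early weight gain, physical activity indoors";
- "Basic dietary intake: Breastfeeding duration, current intake of sweetened beverages";
- three feeding practices: clean-plate policy, tracking of eating, and care not to overfeed.

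Section 2.3 says that "other factors such as infant feeding practices are choices and can be influenced by the WIC program". It adds that infant feeding can affect the propensity for obesity, and that diet and feeding practices act directly on the child's weight. Section 7.5 enters the WIC composites in every model and expects education and food packages to matter for toddler weight.

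The separate Growth model in Table 7-3 has WIC education, food package, time in WIC, birth weight, prematurity and breastfeeding duration. It has no early-gain, beverage or feeding-practice terms.

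**The concern.** A variable that lies between an exposure and the outcome, once held constant, takes its share of the effect out of the exposure's coefficient. If WIC changes weight mainly by changing how children are fed, the route Section 2.3 describes, the WIC coefficients in the Weight model understate its contribution. If breastfeeding changes later weight partly through growth in infancy, the breastfeeding coefficient understates that too.

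Two answers are at stake: the weight part of the sixth objective in Section 1.1 (effect of WIC food packages on outcomes) and the breastfeeding part of question 59 in Table B-1. A small coefficient under the title impact invites the conclusion that WIC or breastfeeding does not matter for weight. Section 7.5 also says that alternative proxies will be tried when a variable is not significant, so an attenuated result could prompt a change of measure.

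**Working it through.** The plan gives no effect size, power or sample-size figure for the weight models, so there is no figure to reproduce. The check compares the specification with the plan's own ordering, then illustrates the consequence.

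**1. Specification against ordering, 12 and 24 months**

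| Exposure | Held constant in Table 7-3 | Ordering in the plan | Omitted from the coefficient |
|---|---|---|---|
| WIC education, food package, time in WIC | Breastfeeding duration, beverages, feeding practices, rapid early gain | Section 2.3: WIC can influence feeding | WIC effect through those terms |
| Breastfeeding duration | Rapid early gain, beverages, feeding practices | Table 7-2 tabulates gain in the first 6 months by breastfeeding | Breastfeeding effect through early gain and later feeding |
| Toddler practices, current beverages | Rapid early gain | Early gain comes first | Nothing by this route; early gain is a plausible confounder |

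**2. Is the total effect available elsewhere?** Only the Weight and Growth models have a weight outcome. The Growth model frees breastfeeding from early gain but conditions the WIC terms on breastfeeding duration. The Table 7-2 cross-tabulations are not adjusted for confounders as a set, a limit Section 7.3 itself acknowledges for cross-tabulations. Chapter 2 mentions simultaneous equations, but Chapter 7 specifies none.

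**3. Illustration in a linear model (all values assumed).** Let the paths be WIC to feeding *a*, feeding to early gain *b*, early gain to later weight/length *c*, and feeding directly to later weight/length *d*.

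- Feeding, early gain not adjusted: *d + bc*. Early gain adjusted: *d*.
- WIC, feeding and early gain not adjusted: *a(d + bc)*. Both adjusted: 0, by construction, because no other WIC route is assumed.

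With *c* = 0.5, *d* = −0.05, *b* from −0.1 to −0.3 and *a* from 0.1 to 0.3:

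- Feeding total: −0.05 + (−0.1)(0.5) = −0.10, to −0.05 + (−0.3)(0.5) = −0.20. Adjusted: −0.05.
- WIC total: 0.1 × −0.10 = −0.01, to 0.3 × −0.20 = −0.06. Adjusted: 0.

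A least-squares simulation with 400,000 observations per scenario agrees. With a binary rapid-gain flag instead of continuous gain, the feeding coefficient is about −0.07 to −0.12, so the flag blocks only part of the path. With an unmeasured common cause of early gain and later weight (path 0.4 to each), the adjusted coefficient is *d* − *b*(0.16/1.16), which is −0.036 at *b* = −0.1 and −0.009 at *b* = −0.3.

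**4. Illustrative power.** If a share *m* is mediated, the linear coefficient is (1 − *m*) times the total. Take a total effect with 80% power at two-sided 0.05, so *z* = 1.96 + 0.84 = 2.80, and hold the standard error fixed:

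- *m* = 0.3: *z* = 1.96, power 0.50
- *m* = 0.5: *z* = 1.40, power 0.29
- *m* = 0.7: *z* = 0.84, power 0.13

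If early gain also removed 30% of residual variance (assumed, ignoring collinearity), *z* is divided by √0.7. Power is then about 0.65 at *m* = 0.3 and 0.39 at *m* = 0.5. This arithmetic applies to the linear model; quantile coefficients need not shrink by the same proportion.

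**The case against.** **The question is studied in segments.** Table B-1 lists ten analyses for question 59. Five are tabulations unadjusted for early gain. The Growth model gives a breastfeeding coefficient without early gain. The sixth objective concerns outcomes generally, and food packages are also set against breastfeeding initiation, breastfeeding intensity and nutrient intake. This stands, and it rules out saying that the pathways are removed from the study. It does not supply an adjusted total WIC effect on weight.

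**Early gain as a mediator is partly inference.** Section 2.3 does not name it as a step between feeding and later weight, and Table 7-3 files it under child health. The inference rests on timing and on the Table 7-2 tabulation by breastfeeding. It is reasonable for breastfeeding only. Early gain precedes toddler practices and current beverages and may shape them, so dropping it for every feeding exposure would introduce confounding. This stands and limits the fix.

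**The list is open.** It is headed as a minimum to explore. That permits change, but a minimum set includes these terms and no alternative is named.

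**Table 7-1.** A reader might take its exclusion of "Interim models that only use a subset of the covariates" as a decision against reduced weight models. It refers to analyses repeated from the previous WIC feeding study. Section 7.5 says the weight and growth models are new, so the exclusion is not evidence about them.

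**Time in WIC.** Section 7.2 builds it partly from days of current participation, which accrue after birth and may depend on earlier feeding. A reduced model does not cure that, so its coefficient needs cautious reading.

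**Conclusion.** The point holds for the 12- and 24-month Weight models. The WIC coefficients are conditional on feeding, diet and early gain, and the breastfeeding coefficient on early gain and later feeding, yet the results are titled impact. The WIC gap is complete in the sense that no specified model gives a confounder-adjusted total effect on weight. The breastfeeding gap is partial, because the Growth model covers the trajectory without early gain.

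The size of the attenuation is unknown. The 30% to 70% shares, the path values and the 80% baseline power are assumptions. A reader might infer that the coefficients will be near zero. The documents do not support that: direct effects remain, diet routes not in the list stay open, and a binary flag blocks only part of the early-gain path. The conclusion rests on Section 2.3's placing of feeding downstream of WIC and on early gain following breastfeeding.

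**What to change.** Keep the full Table 7-3 Weight model and label it a conditional or direct-effect model. For 12 and 24 months, by OLS and quantile regression where each is planned, add:

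1. **WIC model.** WIC composites plus socio-demographic and maternal/family factors fixed before birth, with no feeding, diet or early-gain terms. Use it for the WIC contribution to weight under the sixth objective.
2. **Breastfeeding model.** Breastfeeding duration plus WIC terms and pre-birth and birth factors, without rapid early weight gain, current beverages or toddler feeding practices. Use it for the breastfeeding part of question 59.

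For toddler feeding practices and current beverages, retain early gain as a prior confounder. State in Table 7-2 which model answers which question.

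The cost is plan wording, two extra specifications per age for each method used, and more table columns. No new data are needed.
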